1. INTRODUCTION

The analyses described in this SAP are based upon the following Ionis study documents:

- Study Protocol, Amendment 7 ROW (October 26, 2022)
- Study Protocol, Amendment 8 UK (February 23, 2023)
- Study Protocol, Amendment 6 Germany (December 7, 2021)
- Study Protocol, Amendment 9 France (October 17, 2022)
- Study Protocol, Amendment 9 ROW (August 2, 2023)

This SAP details the procedures for the pharmacokinetic (PK), efficacy and safety statistical methods used to analyze the data.

Any deviations from the final version of this Statistical Analysis Plan (SAP) will be substantiated by sound statistical rationale and will be documented in the final clinical study report.

Revision of this SAP will not be required for any subsequent amendments to the protocol which do not change the analyses described in this SAP. Revisions to specifics such as blood sample collection times, etc. will not require an update to the SAP.

2. STUDY OBJECTIVES

2.1. **Primary Objective**

To evaluate the efficacy of ISIS 678354 (olezarsen) as compared to placebo on the percent change in fasting triglycerides (TG) from Baseline

2.2. Secondary Objectives

To evaluate the efficacy of ISIS 678354 as compared to placebo on the following:

- Percent change in fasting apoC-III from Baseline
- Proportion of patients who achieve $\geq 40\%$ reduction in fasting TG from Baseline
- Percent change in fasting apoB-48 from Baseline
- Percent change in fasting non-HDL-C from Baseline
- Adjudicated acute pancreatitis event rate in patients with a prior history of pancreatitis within 10 years prior to Screening
- Adjudicated acute pancreatitis event rate
- Proportion of patients who achieve \geq 70% reduction in fasting TG from Baseline
- Proportion of patients who achieve fasting $TG \le 880 \text{ mg/dL} (10 \text{ mmol/L})$
- Adjudicated acute pancreatitis event rate in patients with ≥ 2 events of adjudicated acute pancreatitis in 5 years prior to enrollment
- Proportion of patients who achieve fasting $TG \le 500 \text{ mg/dL} (5.7 \text{ mmol/L})$

2.3. Additional/Exploratory Objective(s)

To evaluate the effect of ISIS 678354 as compared to placebo on:

- Patient-reported abdominal pain, other FCS-related symptoms (physical fatigue, difficulty thinking and diarrhea), diet, and impacts, and health-related quality of life (HRQoL), pain interference and cognitive function.
- Emergency room (ER) visits, incidence of all-cause hospitalizations and total inpatient days

3. INVESTIGATIONAL PLAN

3.1. Overall Study Design and Plan

This is a multi-center, randomized, double-blind, placebo-controlled study. Eligible patients will enter an approximately 4-week, but no more than 8-week, Screening Period that includes an at least 2-week Diet Stabilization/Run-In Period for patients not already on a stable diet, and an approximately 2-week Qualification Period. Following qualification, approximately 60 eligible patients will be randomized 1:1 to Cohort A (50 mg) or Cohort B (80 mg) and each cohort further randomized 2:1 to receive ISIS 678354 or placebo in a 53-week Treatment Period. Patients in Cohort A will receive 50 mg of ISIS 678354 once every 4 weeks or matching volume of placebo (0.5 mL) Weeks 1-49, of the Treatment Period. Patients in Cohort B will receive 80 mg ISIS 678354 once every 4 weeks or matching volume of placebo (0.8 mL) Weeks 1-49 of the Treatment Period. Randomization will be stratified by (1) prior history of pancreatitis (within 10 years prior to Screening) and (2) previous treatment with volanesorsen. Dietary counseling will commence at the start of the Diet Stabilization Period and will be reinforced at intervals throughout the Treatment and Follow-up Period. Following the Week 53 visit, eligible patients may elect to enroll in an open-label extension (OLE) study pending study approval by the institutional review board/independent ethics committee (IRB/IEC) and the appropriate regulatory authority. Patients not participating in the OLE will enter the 13-week Post Treatment Evaluation Period. The primary endpoint for the study will be evaluated after the last patient has completed the Week 53/ET visit and will be based on the percent change in fasting TG from Baseline at the primary analysis time point (Month 6).

The study for an individual patient will generally consist of the following periods:

- A screening period of up to 8 weeks is given to complete the screening and baseline assessments. An approximately 4-week but no more than 8-week Screening Period including a Diet Stabilization Period of at least 2 weeks and an approximately 2-week Qualification Period (patients on stable diet, for optimal control of TGs and disease management, known to the Investigator and followed at the site may go from Screening to Qualification without the Diet Run-In Period)
- The Treatment Period is 53 weeks. Eligible patients will have assessments at specified intervals throughout the 53-week Treatment Period. During the Treatment Period, Study Drug is administered by SC injection once every 4 weeks (Week 1 through Week 49).

• The Post-Treatment Follow-up Period is 13 weeks with assessments. Alternatively, following the Week 53 visit, eligible patients may elect to enroll in an OLE study pending study approval of this proposed study by the IRB/IEC and the appropriate regulatory authority.

The End-of-Study is defined as last patient, last visit. For individual patients, End-of-Study is defined as completion of their last study visit.

3.2. Endpoints

The primary analysis time point is at the end of Month 6 where the value is defined as the average of Weeks 23, 25 and 27 assessments.

3.2.1. Primary Endpoints

The primary endpoint is the percent change in fasting TG from Baseline at the primary analysis time point compared to placebo.

3.2.2. Secondary Endpoints

The secondary endpoints include the following:

- Percent change in fasting TG from Baseline at 12 months (average of Weeks 51 and 53) compared to placebo
- Percent change in fasting apoC-III from Baseline at the primary analysis time point compared to placebo
- Percent change in fasting apoC-III from Baseline at 12 months compared to placebo
- Proportion of patients who achieve $\geq 40\%$ reduction in fasting TG from Baseline at the primary analysis time point compared to placebo
- Percent change in fasting apoB-48 from Baseline at the primary analysis time point compared to placebo
- Percent change in fasting non-HDL-C from Baseline at the primary analysis time point compared to placebo
- Adjudicated acute pancreatitis event rate during the Treatment Period (Week 1 through Week 53) compared to placebo, in patients with a prior history of pancreatitis within 10 years prior to Screening
- Adjudicated acute pancreatitis event rate during the Treatment Period (Week 1 through Week 53) compared to placebo
- Adjudicated acute pancreatitis event rate from Week 13 to Week 53 compared to placebo in patients with a prior history of pancreatitis within 10 years prior to Screening
- Adjudicated acute pancreatitis event rate from Week 13 to Week 53 compared to placebo
- Proportion of patients who achieve \geq 70% reduction in fasting TG from Baseline at the primary analysis time point compared to placebo
- Percent change in fasting non-HDL-C from Baseline at 12 months compared to placebo
- Percent change in fasting apoB-48 from Baseline at 12 months compared to placebo
- Proportion of patients who achieve fasting $TG \le 880 \text{ mg/dL}$ at the primary analysis time point compared to placebo

- Adjudicated acute pancreatitis event rate during the Treatment Period (Week 1 through Week 53) compared to placebo, in patients with ≥ 2 events of adjudicated acute pancreatitis in 5 years prior to enrollment
- Adjudicated acute pancreatitis event rate from Week 13 to Week 53 compared to placebo in patients with ≥ 2 events of adjudicated acute pancreatitis in 5 years prior to enrollment
- Proportion of patients who achieve fasting $TG \le 500 \text{ mg/dL}$ at the primary analysis time point compared to placebo

3.2.3. Additional/Exploratory Endpoints

To evaluate the effect of ISIS 678354 as compared to placebo on:

- Patient-reported abdominal pain, other FCS-related symptoms (physical fatigue, difficulty thinking and diarrhea), diet, and impacts, HRQoL, pain interference and cognitive function.
- ER visits, incidence of all-cause hospitalizations and total inpatient days

3.2.4. Safety Variables

Safety and tolerability assessments include adverse events, clinical laboratory tests, electrocardiogram (ECGs), use of concomitant medications, and independently adjudicated event rates of Major Adverse Cardiovascular Events (MACE) for ISIS 678354 as compared to placebo.

4. STATISTICAL METHODS

4.1. Data Management and Quality Assurance

4.1.1. Central Laboratory Data

Ionis Pharmaceuticals, Inc. (Ionis) and Medpace are responsible for the format of the laboratory electronic data transfers and the transfer schedule. Central laboratory data results are not stored in the EDC system. Medpace and Ionis are responsible for the review of the clinical laboratory data. This process involves reviewing the patient and visit identifiers in the central laboratory data results data against the central lab data identifiers collected in the EDC system. Investigator sites have access to the data via lab reports sent directly from the laboratory or through the laboratory's web portal (in which case Investigators only have access to data from their site).

The Sponsor, Investigator and patients will be kept blinded to post-baseline laboratory lipid panel results (TG, apoC-III, total cholesterol, LDL cholesterol, HDL cholesterol, apoB, apoB-48, chylomicron-TG, VLDL, non-HDL-C, and apoA-1) which can jeopardize the blinding of treatment allocation, alter Investigator's clinical practice, or are part of study endpoints to avoid bias in the conduct of the study. Beginning at Week 27, if a patient has an LDL-C > 130 mg/dL (> 100 mg/dL for patients with T2DM or CAD with Baseline LDL-C > 100 mg/dL) on 2 consecutive visits, the LDL-C values for this patient will be unblinded for the remainder of the study.

4.1.2. Pharmacokinetic Data

Ionis is responsible for the management and review of the PK data. This process involves reviewing the patient and visit identifiers with the clinical data collected in the EDC system. The PK data are not stored in the EDC system. Prior to unblinding of the final analysis, any PK concentration datasets provided to Ionis by the bioanalytical lab will be provided without reference to actual patient

ISIS 678354-CS3

identifiers to avoid inadvertent or accidental unblinding. The bioanalytical lab may provide Ionis with datasets containing dummy patient identifiers unrelated to the actual identifiers to allow review of the PK data.

4.1.3. Adjudicated Data

All AEs and SAEs that occur during the study that are consistent with an event of acute pancreatitis will be adjudicated by a blinded, independent committee according to the Atlanta classification of acute pancreatitis (Banks *et al.* 2013) as outlined in the Pancreatitis Adjudication Charter. In addition, data for episodes of acute pancreatitis or suspected pancreatitis in the 5 years prior to enrollment will be collected by review of each patient's medical chart and these events will also be adjudicated.

All AEs and SAEs that occur during the study that are consistent with a MACE will be adjudicated by a blinded, independent committee as outlined in the MACE Adjudication Charter.

4.1.4. Patient Reported Outcome Assessments

The patient reported outcome assessments will be captured by YPrime eCOA System. Patients will enter their assessments into the system using a study-dedicated tablet and handheld devices. Ionis and YPrime are responsible for the format of the electronic data transfers and the transfer schedule. The patient reported outcome assessments will not be stored in the EDC system. Ionis and YPrime are also responsible for the review of the data. This process involves reviewing the patient and visit identifiers in the assessment data against the data identifiers collected in the EDC system. The YPrime system for data collection includes built-in measures to prevent missing items for any completed questionnaire.

4.1.5. Other Data

Genetic lab data will be provided by PreventionGenetics. Platelet antibody data will be provided by Versiti Wisconsin, Inc. Platelet and Immunology Reference Lab. Ionis, PreventionGenetics and Versiti Wisconsin are responsible for the review of the data, the format of the electronic data transfers and the transfer schedule. These data will also not be stored in the EDC system but will be transferred to Ionis as external data.

4.2. General Considerations

4.2.1. Data Presentation

Descriptive summary statistics including n, mean, median, standard error, standard deviation, interquartile range (25th percentile, 75th percentile), range (minimum, maximum) for continuous variables, and counts and percentages for categorical variables will be used to summarize most data. Where appropriate, p-values will be reported. The minimum and maximum will be reported to the same number of decimal places as the raw data recorded in the database. The mean, median, lower quartile and upper quartile will be reported to one more decimal place than the raw data recorded in the database. The SD will be reported to two more decimal places than the raw data recorded in the database. In general, the maximum number of decimal places reported shall be four for any summary statistic.

Categorical data will be summarized in terms of the number of subjects providing data at the relevant time point (n), frequency counts and percentages.

Percentages will be presented to one decimal place. Percentages will not be presented for zero counts. Percentages will be calculated using n as the denominator.

Changes from baseline in categorical data will be summarized using shift tables where appropriate.

All statistical tests will be conducted using 2-sided tests with 5% Type 1 error rates unless otherwise stated. P-values greater than or equal to 0.0001, in general, will be presented to four decimal places. P-values less than 0.0001 will be presented as "< 0.0001".

Confidence intervals will be presented to one more decimal place than the raw data.

Any outliers that are detected during the review of the data before database lock will be investigated. If necessary, queries will be issued to the Investigator, to either correct or confirm the outlier.

The primary endpoint will be assessed on the Full Analysis Set (FAS) and Per Protocol Set (PPS), with the former being the basis for the primary efficacy analysis. The secondary endpoints will be assessed in the FAS. All safety assessments will be performed on the Safety Set (SS). PK endpoints will be assessed in the PK Set as applicable.

Efficacy results will be summarized under the treatment to which patients are randomized. Safety and PK results will be summarized under the treatment which patients actually received. Should there be any cases in which a patient received treatment other than what was randomized, such cases will be discussed in the study report and noted in footnotes where applicable.

All tables and figures containing efficacy endpoints will indicate whether they present raw data or adjusted results from the statistical model, with footnotes indicating the model used and covariates included in the model.

All tables, figures and data listings to be included in the report will be independently checked for consistency, integrity and in accordance with standard Parexel (a CRO that is responsible for pre-programming datasets and TLFs for the Study) procedures.

Missing visits or missing data related to COVID-19 may be provided in the data lstings if supported by data. Additional listings may be provided for all patients impacted by COVID-19 during conduct of the study and additional summary (s) and/or analyses may be provided if deemed necessary.

4.2.2. Baseline Consideration

Baseline for lipid measurements is defined as the average of the pre-dose measurement on Day 1 and the last measurement closest to Day 1 (last measurements from Qualification period and Screening period), prior to administration of the first dose of Study Drug. If 1 of the 2 measurements is missing, then the other measurement will be assigned as the baseline value. If all pre-dose measurements are missing, then the baseline will be set as missing. Missing baseline values will be imputed using the multiple imputation method described in Section 4.9.1.2 in the SAP. Note that if on Day 1, there are multiple pre-dose assessments, then the last assessment with non-missing value will be used as the Day 1 pre-dose assessment.

Baseline consideration for exploratory endpoints:

- 1. Average worst FCS Symptoms (abdominal pain, physical fatigue, difficulty thinking, diarrhea, and composite symptom score): baseline is defined as the average during the screening period and up to Day 1; an alternative baseline is defined as single observation collected at the first day of screening with a two-week recall.
- 2. Highest worst FCS Symptoms: baseline is defined as the highest (worst) score during the screening period and up to Day 1.
- 3. FCS Impacts, PROMIS pain interference, HR-QoL (PROMIS 29+2 Profile v2.1), PROMIS cognitive function, and Patient Global Impression of Severity (PGIS): baseline is defined as the last non-missing assessment on or prior to Day 1

ISIS 678354-CS3

The ECG measurements will be performed in triplicate at each visit. Baseline for continues variables is defined as the average of the last non-missing triplicate prior to the first dose of Study Drug.; Baseline for categorical variable is defined as the worst of the last non-missing triplicate prior to the first dose of Study Drug. If only one or two measurements are available, the baseline will be determined from the available measurements.

The baseline for platelet is defined as the average of all assessments prior to the first dose of Study Drug.

The baseline for other measurements is defined as the last non-missing assessment prior to the first dose of Study Drug.

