3.4. Overall Study Duration and Follow-up

The study for an individual patient will generally consist of the following periods:

- An approximately 4-week, but no more than 8-week, Screening Period including a Diet Stabilization Period of at least 2 weeks and an approximately 2-week Qualification Period (patients on stable diet, for optimal control of TGs and disease management, known to the Investigator and followed at the site may go from Screening to Qualification without the Diet Run-In Period)
- A 53-week Treatment Period during which Study Drug will be administered as a once every 4-week SC injection (Week 1 through Week 49)
- A 13-week Post-Treatment Evaluation Period or transition to OLE Study

Please refer to the Schedule of Procedures in Appendix A.

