4.2.4. Visit Windows

The efficacy and exploratory measures will be mapped to analysis visits according to the visit windows in the table below.

The intent of these visit windows is not to align with those prescribed for visit scheduling in the study protocol but, rather, based on the protocol-defined target study day, to delineate mutually exclusive windows so that all efficacy assessments proximal to a particular study week can be integrated to best represent the patient's status during that period of the study. Visits after Week 53 are part of the post-treatment assessment period and, due to the fact that most patients are expected to roll into the OLE study, these data will only be provided in patient listings for evaluation of individual patient safety rather than being tabulated. Therefore, no visit windows are needed for data analysis for these visits. If a patient discontinued early from the treatment period but attended applicable landmark visits to collect efficacy assessments, then those assessments should be mapped to analysis visits and utilized in the analyses as well, unless otherwise stated.

For Daily FCS Symptoms questionnaire using average, data in the same visit window will be averaged.

For Daily FCS Symptoms questionnaire using the highest (worst) score, the highest score in each visit window will be determined.

For other data, if there are multiple assessments within a visit window, the assessment nearest the target day will be used unless two assessments are equally near, in which case the average value will be used. For lipid data, local lab data will not be used unless central lab assessments are not available at certain visit. When calculating the baseline and analysis endpoints, only if the data from central lab is missing, then the local lab data will be utilized.

ISIS 678354-CS3

Statistical Analysis Plan

Efficacy/PD measure	Nominal Visit (Target Day)	Analysis Visit Window (Day)
Lipid Panel	Week 5 (Day 29)	2-43
	Week 9 (Day 57)	44-71
	Week 13 (Day 85)	72-99
	Week 17 (Day 113)	100-127
	Week 21 (Day141)	128-148
	Week 23 (Day 156)	149-162
	Week 25 (Day 169)	163-176
	Week 27 (Day 183)	177-190
	Week 29 (Day 197)	191-225
	Week 37 (Day 253)	226-281
	Week 45 (Day 309)	282-330
	Week 51 (Day 351)	331-358
	Week 53 (Day 365)	359-379ª
Daily FCS Symptoms	Week 2 (Day 8)	2-8
	Week 3 (Day 15) – Week 53 (Day 365)	(Week-1)*7-5 to (Week-1)*7+1
FCS Impacts; Pain Interference &	Week 5 (Day 29)	2-43
PGIS	Week 9 (Day 57)	44-71

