4.11.3.3. FCS Symptoms

The FCS Symptoms Questionnaire includes 4 items addressing the severity of abdominal pain, physical fatigue, difficulty thinking and diarrhea. These 4 items are administered on a daily basis and ask patients to rate the worst severity of each symptom in the past 24 hours using a 0–10 numeric rating scale. Higher scores denote more severe symptoms.

The daily symptom composite score will be calculated as the average of the non-missing scores across the 4 symptom items. If two or more questions are missing, the symptom composite score will be considered as missing for the day. If one item is missing, then the composite score will be calculated as the average of the 3 non-missing item scores

The data will be mapped to study week based on the visit window specified in Section 4.2.4. The data in the visit window will be averaged and used for summary and analysis. In addition to the weekly average, the highest (worst) response in each week will also be determined and used for summary and analysis. If patients complete less than 4 daily assessments in a week, then the weekly FCS symptom scores will be considered as missing for the week.

Item-level scores and the symptom composite scores, as well as their changes from baseline will be summarized by treatment group and by study week over time using descriptive statistics.

A summary of abdominal pain using the following categories will also be provided: no pain (pain score: 0), mild (pain score: > 0-3), moderate (pain score: > 3-6), or severe (pain score: > 6-10). The frequency and percentage in each category will be tabulated by treatment group and by study week over time.

The change from baseline in the weekly average item and composite scores at the primary analysis time point (average of Weeks 23 to 27) and at Month 12 (average of Weeks 49 to 53) as well as change from baseline in the highest (worst) item and composite scores at the primary analysis time point (worst of Weeks 23 to 27) and at Month 12 (worst of Weeks 49 to 53) will be analyzed using an ANCOVA model with the two stratification factors and treatment group as factors and the corresponding baseline score as a covariate, and will be conducted in the FAS.

The analyses described above will also be repeated using the corresponding FCS symptom collected at the two-week recall administered the first day of screening as the baseline.

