The item and composite scores will be imputed separately

• The Month 6 (primary analysis time point) score will be calculated from the non-missing weekly scores from Weeks 23 to 27 and the Month 12 score will be calculated from the non-missing weekly scores from Weeks 49 to 53. If all weekly scores during the period are missing, the missing score at the primary analysis time point will be imputed using the data from the week that is the closest to Day 169 and within a ± 30 days window, the missing Month 12 data will be imputed using the data from the week that is the closest to the Day 351 and within a ± 30 days window. If 2 or more visits with equal distance, then the average or worst will be used. The item and composite scores will be imputed separately.

ISIS 678354-CS3

Statistical Analysis Plan

The tables below list the summaries and analyses to be performed for the FCS symptom item and composite scores

Observed Data			
Endpoint	Baseline	Post-baseline	Analysis
Average FCS Symptom – item score and composite score	Baseline is defined as the average during the screening period and up to Day 1. If all assessments during the period are missing, the baseline will be considered as missing	Weekly average. If a patient has less than 4 assessments in a week, the weekly score will be considered as missing	 Descriptive statistics of score, change and percent change over time in the FAS Frequency of patients by abdominal pain category (no pain, mild, moderate and severe) over time in the FAS
		Month 6 (Primary analysis time point) - average of Weeks 23 to 27 Month 12 -average of Weeks 49 to 53	 Descriptive statistics of score, change and percent change at Month 6 and Month 12 in the FAS ANCOVA model of change from baseline with the two stratification factors and treatment group as factors, and the corresponding baseline score as a covariate in the FAS Descriptive statistics of abdominal pain score, change and percent change at Month 6 and Month 12 in the subset of FAS patients who reported any abdominal pain (pain score > 0) at Baseline ANCOVA model of change from baseline in abdominal pain score with the two stratification factors and treatment group as factors and the baseline score as a covariate in the subset of FAS patients who reported any abdominal pain (pain score > 0) at Baseline

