	Baseline is defined as the single observation collected at the first day of screening with a two-week recall	Weekly average. If a patient has less than 4 assessments within a week, the weekly score will be considered as missing	Descriptive statistics of score, change and percent change over time in the FAS

ISIS 678354-CS3

Observed Data			
Endpoint	Baseline	Post-baseline	Analysis
Average FCS Symptom – item score and composite score (Continued	Baseline is defined as the single observation collected at the first day of screening with a two-week recall (Continued)	Month 6 (Primary analysis time point) - average of Weeks 23 to 27 Month 12 -average of Weeks 49 to 53	 Descriptive statistics of score, change and percent change at Month 6 and Month 12 in the FAS ANCOVA model of change from baseline with the two stratification factors and treatment group as factors and the corresponding baseline score as a covariate in the FAS
Worst FCS Symptom – item score and composite score	Baseline is defined as the worst during the screening period and up to Day 1. If all assessments during the period are missing, the baseline will be considered as missing	Weekly worst. If a patient has less than 4 assessments in a week, the weekly score will be considered as missing	 Descriptive statistics of score, change and percent change over time in the FAS Frequency of patients by abdominal pain category (no pain, mild, moderate and severe) over time in the FAS
		Month 6 (Primary analysis time point) - worst of Weeks 23 to 27	 Descriptive statistics of score, change and percent change at Month 6 and Month 12 in the FAS
		Month 12 -worst of Weeks 49 to 53	2. ANCOVA model of change from baseline with the two stratification factors and treatment group as factors and the corresponding baseline score as a covariate on FAS
			 Descriptive statistics of abdominal pain score, change and percent change at Month 6 and Month 12 in the subset of ITT patients who reported any abdominal pain (pain score > 0) at Baseline
			 ANCOVA model of change from baseline in abdominal pain score with the two stratification factors and treatment group as factors and the baseline score as a covariate in the subset of ITT patients who reported any abdominal pain (pain score > 0) at Baseline

ISIS 678354-CS3

Observed Data			
Endpoint	Baseline	Post-baseline	Analysis

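### Worst-score FCS symptom baseline is a maximum over all of screening, while the weekly worst is a 7-day maximum, so weekly change summaries show improvement in every arm with no true change

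*Combined protocol and SAP*

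**What the plan says.** **Baseline.** SAP 4.2.2 sets it thus: "Highest worst FCS Symptoms: baseline is defined as the highest (worst) score during the screening period and up to Day 1". The observed-data table in SAP 4.11.3.3 repeats the rule ("Baseline is defined as the worst during the screening period and up to Day 1") and treats baseline as missing only when every assessment in the period is missing. No minimum number of diary entries applies.

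**Length of screening.** Protocol 3.4 describes "An approximately 4-week, but no more than 8-week, Screening Period including a Diet Stabilization Period of at least 2 weeks". SAP 3.1 gives the same length, and adds that patients on a stable diet who are already followed at the site "may go from Screening to Qualification without the Diet Run-In Period".

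**On-treatment values.** These take three forms.
- Weekly: "the highest (worst) response in each week will also be determined and used for summary and analysis" (SAP 4.11.3.3), taken within the visit windows of SAP 4.2.4. A week with fewer than 4 daily entries is missing. The SAP table plans descriptive change and percent change of this weekly worst over time.
- Month 6 and Month 12: the worst of Weeks 23 to 27 and of Weeks 49 to 53. The ANCOVA uses these values, with the corresponding baseline score as covariate.
- Imputed-data analysis only, for a patient with none of the five weekly scores: "the missing score at the primary analysis time point will be imputed using the data from the week that is the closest to Day 169". The substituted week has to lie no more than 30 days away. Month 12 is handled the same way around Day 351.

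**The concern.** An expected maximum depends on how many days it covers. If a symptom is unchanged, the worst of 28 to 56 days cannot be expected to fall below the worst of 7 days, and for an episodic symptom it will usually be clearly higher. Subtracting the long-window baseline from a 7-day worst therefore gives a negative mean change in each arm. A reader of the weekly tables for worst abdominal pain, fatigue, difficulty thinking or diarrhea could take this as relief on treatment, or as a large placebo response.

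The imputed-data analysis raises a related problem: a one-week maximum is placed beside other patients' five-week maxima. A Month 6 or Month 12 value that rests on only one or two valid weeks is lowered in the same way. Missing diary weeks then look like benefit.

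**Working it through.** The plan states no power or expected size for this endpoint, so there is no figure to reproduce. The check compares window lengths and then expected maxima under no change.

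**Window lengths.** SAP 4.2.4 sets the daily-diary window for week w as Day (w−1)×7−5 to Day (w−1)×7+1, which is 7 days.
- Week 23 starts on 22×7−5 = Day 149; Week 27 ends on 26×7+1 = Day 183. Month 6 covers 183−149+1 = 35 days.
- Week 49 starts on 48×7−5 = Day 331; Week 53 ends on 52×7+1 = Day 365. Month 12 covers 35 days.
- Baseline: about 4×7 = 28 days, at most 8×7 = 56 days, varying by patient.

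**Exact calculation for a simple pattern.** Assumptions, not in the documents: days are independent, the symptom occurs on a share p of days, and its score is then uniform on 1 to 8. Then

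E[max over n days] = Σ (k = 1 to 8) {1 − [1 − p(9−k)/8]^n}.

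For p = 0.1 and n = 7 the terms are 0.522 + 0.473 + 0.421 + 0.364 + 0.302 + 0.235 + 0.162 + 0.084 = 2.56.

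| p | 7 days | 14 days | 28 days | 35 days | 56 days |
|---|---|---|---|---|---|
| 10% | 2.56 | 4.14 | 5.82 | 6.28 | 7.04 |
| 30% | 5.30 | 6.68 | 7.49 | 7.65 | 7.87 |
| 60% | 6.79 | 7.52 | 7.88 | 7.93 | 7.99 |

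Apparent change with no true change, in the order p = 10%, 30%, 60%:
- Weekly worst (7 days) against a 28-day baseline: 2.56−5.82 = −3.26; 5.30−7.49 = −2.19; 6.79−7.88 = −1.09.
- Weekly worst against a 56-day baseline: −4.48; −2.57; −1.20.
- Month 6/12 worst (35 days) against a 28-day baseline: +0.46; +0.16; +0.05.
- Month 6/12 worst against a 56-day baseline: −0.76; −0.22; −0.06.
- One week standing in for five (7 against 35 days): −3.72; −2.35; −1.14.
- Two valid weeks instead of five (14 against 35 days): −2.14; −0.97; −0.41.

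**Other patterns.** Simulating the same pattern with day-to-day latent correlation from 0 to 0.5 gives a weekly shift of −1.1 to −4.6 points across the three frequencies. A different model assumes 0.25 to 4 episodes per 28 days varying between patients, 1 to 3 days each, severity 2 to 10, and a low background. It gives:
- 7-day worst: −0.9 to −2.6 against a 28-day baseline, and −1.7 to −3.9 against a 56-day baseline;
- 35-day worst: +0.2 to +0.5 against 28 days, about 0 against 35 days, −0.2 to −0.4 against 42 days, and −0.6 to −1.0 against 56 days.

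If skipping the run-in shortened screening to 14 days (an assumption), the episode model gives −0.3 to −1.3 for the weekly value and +0.8 to +1.8 for the 35-day value.

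**Between-arm check.** Using the episode model at one episode per 28 days, 21 against 21 patients, screening lengths mixed from 28 to 56 days and complete diaries, 4,000 null ANCOVAs gave a mean difference of +0.01 points (35-day outcome) and −0.02 (7-day outcome). Type I error was 4.6% and 5.0%.

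**Unequal diary completion (illustration only).** Suppose 20% of one arm and 5% of the other had only one or two valid weeks, half each. With the exact figures, the spurious difference is 0.15 × (3.72+2.14)/2 = 0.44 points at p = 10%, 0.15 × (2.35+0.97)/2 = 0.25 at 30%, and 0.15 × (1.14+0.41)/2 = 0.12 at 60%. Baseline adjustment does not remove this, because the distortion lies in the outcome.

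**The case against.** The strongest reply is that the comparisons the SAP actually models are not 7-day values. Month 6 and Month 12 are 35-day maxima, inside the 28 to 56 day range of the baseline, and the ANCOVA adjusts for that baseline. This stands. The residual shift there is small and changes sign with screening length, and the null ANCOVA shows no between-arm bias under equal completion.

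The substitution is also narrow. It belongs to the additional imputed-data analysis, needs all five weeks missing, and takes a week close by. Losing one week of five (35 to 28 days) moves the expected maximum by only 0.05 to 0.46 points. That stands too, so the effect matters mainly for values resting on one or two weeks.

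The SAP further plans average-score analyses, whose expected value does not depend on window length, and repeats the analyses with the two-week-recall baseline. The recall baseline gives every patient the same window, but two weeks match neither 7 nor 35 days, so it does not repair the weekly summaries.

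Finally, the endpoints are exploratory and the weekly changes are descriptive and shown by arm, with placebo alongside. This limits the stakes but does not correct the within-arm numbers.

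**Conclusion.** The baseline rule is wrong for the weekly change summaries, as a minor, exploratory matter. The direction follows from window length alone for a symptom that is stable over time. The size, about 1 to 4 points of apparent improvement on the 0-10 scale, rests on assumed symptom patterns that the documents do not give. The single-week substitution, and Month 6/12 maxima resting on one or two valid weeks, are lowered in the same way.

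A reader might infer more: that worst scores improve by construction at Month 6 and Month 12 as well, or that the treatment comparison is biased. The documents do not support either. Against 35-day maxima, a 4-week screening gives slight apparent worsening, about 35 days gives none, and only longer screening gives slight improvement. Between-arm bias would need diary completeness to differ by arm, and nothing in the documents shows that it does. Nor does the diet run-in affect every patient's baseline, since some may skip it.

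**What to change.** - **Weekly change summaries:** define baseline as the mean of the weekly worst scores over pre-dose 7-day windows, with the same rule of at least 4 entries per week.
- **Month 6 and Month 12, at least in the imputed-data analysis:** use the mean of the valid weekly worst scores over Weeks 23 to 27 and Weeks 49 to 53, against that same baseline. A mean of weekly maxima has the same expectation as one week's maximum when symptoms are stable, so a substituted week is then on the right scale.
- **Period maximum:** keep it as a supplementary summary if the isolated severe episode is of interest, because the mean of weekly worsts is a different quantity.

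The cost is SAP wording and a changed derivation; no new data are needed. Within-arm improvement in worst scores will look less favourable, and a few patients with sparse screening diaries may lack a baseline. Weeks with 4 entries will still have a lower expected maximum than weeks with 7 (1.62 against 2.56 at p = 10%, by the formula above with n = 4), but the same rule then applies before and after dosing.
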